## Executive Summary

### NEED

*There is a paucity of data on the wear experience of DAILIES TOTAL1 Multifocal contact lenses in a population that has previously worn INFUSE One-Day Multifocal.*

### STUDY OBJECTIVE

*The purpose of this study is to determine the comfort and vision of DAILIES TOTAL1 Multifocal contact lenses in a population of satisfied INFUSE One-Day Multifocal contact lens wearers*

### STUDY HYPOTHESIS

*A high proportion ( $\geq 70\%$ ) of satisfied INFUSE One-Day Multifocal wearers will report asymptomatic dry eye status (CLDEQ-8  $< 12$ ) after 2 weeks of wear with DAILIES TOTAL1 Multifocal (DT1MF).*

### SUPPORTS CLINICAL MESSAGE

*DAILIES TOTAL1 Multifocal provides excellent comfort, vision and satisfaction in satisfied INFUSE One-Day Multifocal wearers. A majority of patients would like to continue wearing the lens. X out of 10 would recommend to a friend/family.*

### STUDY DESIGN

Cohort	Endpoints	
30 presbyopic, current satisfied INFUSE One-Day Multifocal contact lens wearers		
Primary: The proportion of participants with CLDEQ-8 <math>< 12</math> after 2-weeks of wearing DAILIES TOTAL1 Multifocal (w finalized prescription)
 
Secondary:
 
 
1. VAS in comfort, overall vision and satisfaction
 
2. CLDEQ-8 score after two weeks of DT1MF wearing
 
3. Other Likert statement related to experience with study lenses
 
4. SANDE and satisfaction ratings after two weeks
 
5. Functional scores using WPAI-SHP after two weeks
 
6. Distance, intermediate and near binocular VA at baseline (with Infuse MF) and after two weeks (with DT1MF)
 
 
Exploratory:
 
 
1. Digital device average usage time with CLs
 

Alcon Product	DAILIES TOTAL1 Multifocal	Design	Prospective, open-label, single arm study
Comparator	N/A	Time of follow-up	21 days
STATISTICAL ANALYSIS Descriptive statistical analysis (please see slide 11 on detailed statistical plan/analysis) SAMPLE SIZE 30 subjects (33 subjects to account for drop out) STUDY DURATION (Contract execution to CSR) 9 months			
Strategic Imperative SI-x: How does DAILIES TOTAL1 Multifocal perform in satisfied Infuse One-Day Multifocal (Ultra One-Day Multifocal) wearers? RTI 26-CL032 Target abstract presentation date: AOA/AAOpt 2027 Target manuscript submission date: Contact Lens and Anterior Eye (CLAE)/Clinical Optometry 2027 Grant Request IIT Budget: \$126,105.00 USD Funding Source: Regional Funding Timeline: Q2 2026 to Q1 2027			

## Study Background & Unmet Medical Need

### Background:

Despite advancements in contact lens (CL) technology, presbyopic patients often experience discomfort and dissatisfaction, leading to high dropout rates. This study aims to determine the success rate of refitting current, satisfied wearers of Bausch + Lomb Infuse Multifocal (kalifilcon A) contact lenses into DAILIES TOTAL1 Multifocal (delefilcon A) contact lenses. The goal is to understand how satisfied multifocal CL wearers respond to being refitted into an alternative daily disposable CL brand with different material properties and designs. This information will be valuable for clinicians when considering transitions due to patient preference, cost, material discontinuation, or the availability of newer technologies.

### Unmet Medical Need:

There is a paucity of data on the wear experience of DAILIES TOTAL1 Multifocal contact lenses in a population that has previously worn INFUSE One-Day Multifocal. While existing multifocal lenses provide adequate refractive correction, they often fail to maintain the complex biochemical homeostasis of the aging tear film, leading to significant "end-of-day" discomfort and fluctuating vision as the lens surface dehydrates. There remains a critical clinical need for a lens material that doesn't simply offer physical lubrication but actively mimics the eye's natural environment—either through a high-oxygen water gradient surface to minimize mechanical friction or the infusion of osmoprotectants and electrolytes to prevent hyperosmotic stress. This study addresses the gap in providing a sustainable, all-day wearing experience that preserves both physiological health and the precise optical clarity required for multifocal success.

## Study Design & Methodology

### Study Design

Prospective, open-label, single-arm refit study. Participants serve as their own control for exploratory endpoints using paired baseline and follow-up measures. No washout period is required to preserve real-world ecological validity.

Study duration per participant: approximately 3 weeks

### Methodology:

#### Procedures

##### Visit 1 — Baseline/ Dispense

- Informed consent
- Eligibility verification (including confirm satisfaction with current InfuseMF)

Subjects will be asked the following question: “**Are you satisfied with your current (Infuse MF) contact lenses?**” Subjects must answer ‘yes’ to continue in study.

- CLDEQ-8 baseline assessment
- SANDE (Symptom Assessment in Dry Eye)
- WPAI-SHP (Work Productivity and Activity Impairment Questionnaire)
- Power and ADD of habitual Infuse lenses
- Visual Acuity (VA) High-contrast LogMAR visual acuity measured at distance (20ft), intermediate (60cm), and near (40cm) with Infuse MF
- Daily average time of digital device usage while wearing habitual contact lenses (including tablet, phone, computer, TV and etc)
- Manifest Refraction
  - Refit into DAILIES TOTAL1 Multifocal
- Visual Acuity (VA) High-contrast LogMAR visual acuity measured at distance (20ft), intermediate (60cm), and near (40cm) with DT1 MF
- DT1mf Lens dispense

##### Visit 2 – Week 1 Follow-up visit (1 week after V1)

- Patient will follow up at 1 week in case power adjustment is needed, as determined by the PI

##### Visit 3— Week 3 Follow-up/Exit (2 weeks after V2)

- CLDEQ-8
- SANDE
- WPAI-SHP

- Satisfaction survey; intent to continue wearing, recommend Likert questions
  - Daily average time of digital device usage while wearing study contact lenses (including tablet, phone, computer, TV and etc)
  - Visual Acuity (VA) High-contrast LogMAR visual acuity is measured at distance (20ft), intermediate (60cm), and near (40cm) with DT1 MF.
- Safety evaluation

To outline the important study considerations for the DT1 Multifocal refit trial among habitual Infuse MF wearers, the methodology must account for the high expectations of a "satisfied" baseline population. The following summary details the key procedural considerations required to derive valid endpoints.

## **Study Considerations:**

### **1. Longitudinal Baseline Control**

Consideration: Baseline assessments (Visit 1) must be performed while the subject is wearing their habitual Infuse Multifocal lenses to capture a "satisfied" state of ocular comfort and visual acuity before the intervention.

### **2. Standardized Fitting Approach**

To minimize investigator bias and ensure "First-Lens Fit Success," the study must strictly follow the manufacturer's fitting guidelines for DAILIES TOTAL1 (DT1) Multifocal.

Consideration: Refitting involves matching the effective power and add levels of the habitual lens to the corresponding DT1 parameters. A mandatory approximately 15-minute equilibration period is required before performing over-refraction to allow the new study lenses to stabilize on the eye.

### **3. Multi-Domain Subjective Assessment**

The methodology employs three distinct validated instruments to capture different aspects of the patient experience:

CLDEQ-8 (Contact Lens Dry Eye Questionnaire-8): Focuses on lens-specific discomfort and end-of-day dryness. It evaluates the frequency and intensity of dryness and discomfort, as well as the frequency of "closing your eyes" due to lens awareness. A decrease of  $\geq 3$  points from the Infuse baseline to the DT1 follow-up is considered a clinically meaningful improvement in comfort.

SANDE (Symptom Assessment in Dry Eye): Captures the global frequency and severity of symptoms using a 100 Visual Analog Scale (VAS). The SANDE score provides a sensitive measure of "global" symptom shifts that may not be captured by lens-specific tools.

WPAI-SHP (Work Productivity and Activity Impairment-Specific Health Problem): Evaluates the functional impact of lens wear on work productivity and daily activities. The WPAI-SHP quantifies the impact of "contact lens discomfort" on work productivity. It specifically measures "Presenteeism" (reduced productivity while working) and "Activity Impairment". This assesses if the material properties of DT1 MF lead to a functional "real-world" benefit, such as increased comfort during sustained computer use.

Likert scales on satisfaction, intent to purchase and willingness to recommend to friend and family will also be collected

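### The WPAI-SHP sentence credits lens material, but the paired Infuse-to-DT1MF change measures the whole refit: material, optical design and any prescription update

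*Protocol*

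**What the plan says.** Under Study Considerations, item 3 (Multi-Domain Subjective Assessment), the WPAI-SHP paragraph ends: "This assesses if the material properties of DT1 MF lead to a functional 'real-world' benefit, such as increased comfort during sustained computer use". The same item treats a CLDEQ-8 fall of at least 3 points from the Infuse baseline as a meaningful gain in comfort.

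The Study Design section states: "Participants serve as their own control for exploratory endpoints using paired baseline and follow-up measures". The Executive Summary's sixth secondary endpoint sets binocular acuity with Infuse at baseline beside acuity with DT1MF after two weeks.

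On the prescription behind each measurement:

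- **Infuse.** Item 1 of Study Considerations says "Baseline assessments (Visit 1) must be performed while the subject is wearing their habitual Infuse Multifocal lenses". The Visit 1 list includes "Power and ADD of habitual Infuse lenses".
- **DT1MF starting power.** Item 2 says "Refitting involves matching the effective power and add levels of the habitual lens to the corresponding DT1 parameters". It also provides for an over-refraction once the lenses have settled for about 15 minutes.
- **DT1MF later power.** The Visit 2 text reads "Patient will follow up at 1 week in case power adjustment is needed, as determined by the PI". The assessment table repeats this. Item 5 then requires 14 days on the finalized prescription before outcomes are read.

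The Background section says the two brands differ in both material and design.

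**The concern.** The two sides of the within-person comparison are not in the same prescription state. Infuse is assessed at whatever power the participant arrives with. DT1MF is assessed after a refraction, an over-refraction and, where needed, a further power change. Add needs change over time in presbyopes, so a sphere or add update alone could improve intermediate or near focus and hence ease at a computer, which is the example the WPAI-SHP sentence gives. It could also improve acuity and the CLDEQ-8 blur items.

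A single-arm study with no Infuse period on an equally updated prescription cannot separate that update from the lens. Nor can it separate material from optical design, because every participant changes both together. At stake is what the report may say about paired change: that the refit was followed by it, or that the DT1MF material caused it.

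**Working it through.** There is no plan figure to reproduce; the point is one of attribution. The check traces the visit sequence and then bounds the possible size under stated assumptions.

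**1. Infuse side.** The Visit 1 list puts the questionnaires, the habitual power and add, and Infuse acuity before "Manifest Refraction". Nothing compares the habitual power with that refraction or updates it before baseline is recorded. Eligibility asks for best-corrected distance acuity and at least 30 days of wear. It sets no acuity limit through the Infuse lenses at any distance.

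**2. DT1MF side.** The starting power is matched to the habitual lens. There are then two opportunities to move away from it: over-refraction at Visit 1 and the conditional adjustment at Visit 2.

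**3. What a paired change contains.** Leaving aside time and selection effects:

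change = material + optical design + prescription update.

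One change is observed per participant, and no participant receives the material without the design. Even where the update is zero, the first two terms cannot be separated.

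**4. Vision content of the CLDEQ-8** (item scales in the Appendix).
- Maximum score: 4+5+4+5+4+5+4+6 = 37.
- The two changeable-vision items give 4+5 = 9, and 9/37 = 24%.
- Entry requires a score below 12, so the baseline is at most 11. The last item scores at least 1, so the largest possible fall is 11 − 1 = 10.
- A 3-point fall needs a baseline of at least 4 and could come from the vision items alone.

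**5. Size of a prescription-only shift.** The documents give neither the share of participants whose power changes nor its effect, so all inputs here are assumptions. Mean shift = share updated × gain per updated participant.
- CLDEQ-8: 0.20 × 1 = 0.2 points, up to 0.60 × 3 = 1.8 points.
- Acuity: 0.20 × 0.10 = 0.02 logMAR, up to 0.50 × 0.15 = 0.075 logMAR. At 0.02 logMAR per letter that is 1 to 3.75 letters.
- If no power is changed, the shift is zero. The upper ends are generous for a population that enters satisfied and with low scores.

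**6. If a paired test were run.** The statistical section plans description, although the sample size text mentions parametric testing. Take n = 30, a two-sided paired t-test at 5%, no lens effect, and a prescription-driven shift of d standard deviations of the paired difference. The noncentrality is d√30 with 29 degrees of freedom.

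| d (assumed) | d√30 | Chance of p < 0.05 |
|---|---|---|
| 0.1 | 0.55 | 8% |
| 0.2 | 1.10 | 19% |
| 0.3 | 1.64 | 36% |
| 0.5 | 2.74 | 75% |

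This shows sensitivity only; it does not estimate what will happen.

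**The case against.** The strongest reply is that the refit is the intervention. The protocol calls itself a single-arm refit study and aims to learn how often refitting succeeds. Refraction and power adjustment belong to refitting, so measuring the package answers the stated question. That stands, and it is the reason the WPAI-SHP sentence should name the package and not one ingredient.

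Several further points limit the concern:

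- **Matching.** The DT1MF starting power is tied to the habitual lens, and the Visit 2 change is conditional. A reader might infer that a stale Infuse prescription is routinely set against a fresh DT1MF one. The documents do not support that; they only leave room for it.
- **Entry filters.** Participants must say they are satisfied with Infuse and score below 12 on an instrument that includes the blur items. This screens out some symptomatic under-correction, though neither filter verifies the power.
- **Scope of the sentence.** It closes the WPAI-SHP paragraph, and that instrument asks about lens discomfort, not vision. It does not attribute acuity or CLDEQ-8 change to material. Those outcomes are affected only in so far as they are read as paired lens comparisons.
- **Weight in the plan.** Own-control use is stated for exploratory endpoints, of which only device time is listed. The Study Endpoints section gives the secondary outcomes after two weeks, and no paired test is specified. Still, the Executive Summary's acuity endpoint and the 3-point CLDEQ-8 rule do invite a paired reading.
- **Direction.** A reader might infer that the bias can only favour DT1MF. Selecting on a baseline CLDEQ-8 below 12 invites regression to the mean in the opposite direction. A Visit 2 change may also compensate for the DT1MF optics without correcting an outdated prescription.

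Exploratory status excuses low precision. It does not make a causal attribution identifiable.

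**Conclusion.** The attribution to material is not supportable under this design. A paired change in WPAI-SHP, CLDEQ-8, SANDE or acuity is the effect of the refit as a whole: material, optical design and any prescription update. This follows from the visit sequence and the absence of a comparison arm, and needs no numerical assumption.

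The size of the prescription component is unknown. It probably favours DT1MF, with matching and the entry filters limiting it, and the net direction of CLDEQ-8 change is uncertain because of the baseline selection. The ranges in the working rest wholly on assumed inputs and include zero.

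A reader might also infer that the headline result is compromised. It is not: the primary endpoint is the proportion below 12 on DT1MF, with no Infuse contrast. The VAS and Likert items have no Infuse baseline, so no paired comparison arises for them. The point is a correction to wording and reporting.

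**What to change.** 1. In the WPAI-SHP paragraph, replace the reference to the lens's material properties with: *the refit into DT1 MF (lens material, optical design and any prescription update)*. Describe every paired change the same way in the report.
2. Report descriptively the difference in power and add between the habitual Infuse lenses and the final DT1MF lenses. The visit lists name the Infuse power and add; name the final DT1MF power and add as recorded items too.
3. If paired results are split, define the groups from Visit 1 data only, by comparing habitual Infuse power and add with the Visit 1 manifest refraction. Fix the rule for agreement in advance and label the split descriptive.

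Grouping by final DT1MF power is tempting but unsound. That power is settled after a week of DT1MF wear, so participants doing poorly are more likely to be adjusted, and the split would select on response. Nor would an unchanged-power group isolate material, since the optical design still differs.

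Cost: a wording change and one or two descriptive tables, with no new visit or procedure. The material claim is given up, and with 30 completers the subgroups will be small.

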#### **4. Subjective Surface Monitoring**

A critical safety consideration is the assessment of the corneal epithelium during the material transition from Kalifilcon A to Delefilcon A.

Consideration: Corneal Fluorescein Staining (CFS) is performed at baseline (inclusion/exclusion) and Day 21 (safety evaluation). Sodium fluorescein is instilled to evaluate the integrity of the corneal epithelium. Staining is graded using the NEI/Industry scale, which divides the cornea into five zones (Superior, Inferior, Temporal, Nasal, and Central), each graded from 0 to 3.

#### **5. Wash-in / Adaptation Period**

The study allows for a 14-day wearing period of the finalized prescription before the final endpoint derivation.

Consideration: This duration is essential to move past the "novelty effect" of a new lens and to allow the ocular surface to adapt to the new study lens, ensuring the data reflects long-term wearability.

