### Primary Endpoint:

- The proportion of participants with CLDEQ-8 <12 after 2-weeks of wearing DAILIES TOTAL1 Multifocal (w finalized prescription)

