## Study Assessments

	Visit 1 Baseline	Visit 2 (~1 week after V1)	Visit 3 (~2 weeks after V2*
Informed Consent	X		
Eligibility Confirmation	X		
CLDEQ-8	X		X
SANDE	X		X
WPAI-SHP	X		X
DT1 MF Lens Fitting & Dispense	X	X (PI to optimize the power if needed)	
VAS, satisfaction Survey and other Likert statements			X
Safety Assessment		X	X

\*After wearing the finalized prescription

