## CLDEQ-8

### CONTACT LENS QUESTIONNAIRE-8 (CLDEQ-8)

#### 1. Questions about EYE DISCOMFORT:

- a. During a typical day in the past 2 weeks, how often did your eyes feel discomfort while wearing your contact lenses?

- 0 Never
- 1 Rarely
- 2 Sometimes
- 3 Frequently
- 4 Constantly

When your eyes felt discomfort with your contact lenses, how intense was this feeling of discomfort...

- b. At the end of your wearing time?

Never have it	Not at All Intense				Very Intense
0	1	2	3	4	5

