#### 2. Questions about EYE DRYNESS:

- a. During a typical day in the past 2 weeks, how often did your eyes feel dry?

- 0 Never
- 1 Rarely
- 2 Sometimes
- 3 Frequently
- 4 Constantly

When your eyes felt dry, how intense was this feeling of dryness...

- b. At the end of your wearing time?

Never have it	Not at All Intense				Very Intense
0	1	2	3	4	5

Patient/Subject #: \_\_\_\_\_

Date: \_\_\_\_/\_\_\_\_/\_\_\_\_ Time: \_\_\_\_\_

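### The 14 days the protocol calls a wash-in are the same 14 days the Visit 3 CLDEQ-8 asks about, so they are not a wash-in for the primary endpoint, and about 21 days of wear cannot support the long-term claim

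*Protocol*

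**What the plan says.** The protocol's Study Considerations, item 5 (Wash-in / Adaptation Period), states: "The study allows for a 14-day wearing period of the finalized prescription before the final endpoint derivation". It calls this duration essential for moving beyond the novelty of a new lens and says it will "allow the ocular surface to adapt to the new study lens, ensuring the data reflects long-term wearability".

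The Primary Endpoint section defines the endpoint as "The proportion of participants with CLDEQ-8 <12 after 2-weeks of wearing DAILIES TOTAL1 Multifocal (w finalized prescription"). The Methodology section labels the endpoint visit "Week 3 Follow-up/Exit (2 weeks after V2"). The Study Assessments table gives the same interval only as approximate, with the footnote "After wearing the finalized prescription".

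The CLDEQ-8 is reproduced in the Appendix. Its discomfort group opens "During a typical day in the past 2 weeks, how often did your eyes feel discomfort while wearing your contact lenses", and its dryness group "During a typical day in the past 2 weeks, how often did your eyes feel dry". The groups on changeable vision, closing the eyes and removing the lenses use the same two-week recall.

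Study lenses are first dispensed at Visit 1. Visit 2 follows one week later, and power is changed there only if the investigator finds it necessary. The Executive Summary gives follow-up as 21 days.

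**The concern.** A wash-in is time that passes before the measured period and is not itself measured. For an instrument that asks about the present moment, 14 days of wear before the visit would serve. The CLDEQ-8 looks back two weeks, so 14 days of wear before the visit is the measured period itself. The protocol therefore claims a property, that the primary score comes from after the adaptation period, which its own instrument and schedule do not provide.

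Two things are at stake. The first is the claim: the study is meant to support a clinical message and a manuscript, and a statement that the data reflect long-term wear could be carried into either. The second is the match between the score and the endpoint. The endpoint is tied to the finalized prescription, but the assessment table gives Visit 3 only an approximate time and no minimum interval. An early visit by a participant whose power was changed would bring days on the superseded power into the recall.

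**Working it through.** This is calendar arithmetic; no sample-size formula is involved.

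**Inputs**
- Visit 1, first dispense: day 0 (Methodology).
- Visit 2: one week later, day 7 (Methodology).
- Visit 3: two weeks after Visit 2 (Methodology).
- Stated wash-in: 14 days on the finalized prescription (Study Considerations, item 5).
- CLDEQ-8 recall: past two weeks, 14 days (Appendix).
- Stated follow-up: 21 days (Executive Summary).

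**Step 1. Reproduce the stated figure.** Visit 3 = 7 + 14 = day 21. This agrees with the 21 days in the protocol.

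**Step 2. Overlap of recall and wash-in.**
- Recall window: from 21 − 14 = day 7 to day 21.
- Wash-in: from Visit 2 (day 7) to Visit 3 (day 21).
- Overlap: 14 of 14 days (100%). Days on the finalized prescription after Visit 2 and before recall starts: 14 − 14 = 0.

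**Step 3. What does lie outside the recall.** Days 0 to 7 of study-lens wear do not overlap the recall at all. Every participant therefore has 7 days in the study lens before the recall begins. If power is unchanged at Visit 2, those 7 days were on the same prescription. If power is changed, they were on a different one, and no wear of the final power precedes the recall.

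**Step 4. Sensitivity to the approximate Visit 3 timing.** Recall days that precede Visit 2 = 14 − (days from Visit 2 to Visit 3), when positive. The protocol gives no visit window, so the intervals below are assumptions.

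| Visit 3, days after Visit 2 | Recall days before Visit 2 | Share of recall | Days after Visit 2 but before recall |
|---|---|---|---|
| 10 | 4 | 4/14 = 29% | 0 |
| 12 | 2 | 2/14 = 14% | 0 |
| 13 | 1 | 1/14 = 7% | 0 |
| 14 | 0 | 0% | 0 |
| 15 | 0 | 0% | 1 |
| 17 | 0 | 0% | 3 |

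The days before Visit 2 concern a superseded power only for participants whose power was changed. The protocol does not give that share, so it could lie anywhere from 0 to 100%.

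**Step 5. What a separate wash-in would need.** Visit 3 study day = 7 + wash-in + 14. With 7 days of wash-in after Visit 2 this is day 28, and with 14 days it is day 35. This shows the arithmetic only and is not a proposed schedule.

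**The case against.** The best defence is that adaptation to the new lens starts at Visit 1, not at Visit 2. The first week of wear is outside the recall for everyone, and a participant with unchanged power has by then worn the same prescription for seven days. The primary endpoint is also defined as two weeks on the finalized prescription. A two-week recall taken two weeks after finalization fits that definition and keeps earlier wear out. The objective, the hypothesis and the endpoint list make no long-term claim. All of this stands. It limits the fault to the rationale paragraph and the loose visit timing, but it does not make the 14 days a wash-in.

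A reader might infer more than the documents support:

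- **That the primary endpoint averages over adaptation and is uninterpretable.** The frequency items on discomfort, dryness, vision and closing the eyes ask about a typical day. Only the lens-removal item asks about frequency over the whole two weeks. The score has a clear meaning as a rating of those two weeks.
- **That no time after adaptation is observed, or that the success rate is biased.** The protocol gives no length for adaptation apart from the 14-day period itself. If it takes a week or less, the recall of participants with unchanged power lies wholly after it. Novelty could raise the proportion and adaptation symptoms could lower it; neither can be quantified.
- **That 14% or 29% of the primary data concern the wrong prescription.** Those figures are shares of one person's recall at assumed visit days. They apply only to early attenders with a changed power and are not effects on the proportion. The Methodology section and item 5 both say two weeks or 14 days; only the assessment table is approximate. The Appendix also opens by telling subjects to rate their most recent pair of study lenses. That instruction stands directly above the VAS, so its reach to the CLDEQ-8 is unclear, but it may lessen the problem.
- **That 21 days is too short because 30 days of Infuse wear are required.** The 30 days are an eligibility rule for habitual wear, not a benchmark for adaptation.

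**Conclusion.** The point holds as a wrong statement about the design. On the planned schedule, 14 of 14 recall days fall in the period labelled wash-in, and no days on the finalized prescription after Visit 2 precede the recall. Total wear of the study lens is about 21 days with nothing measured later, so the data cannot be said to ensure a reflection of long-term wear. The one exempt interval is the first week, and for participants with a changed power that week was on a different prescription.

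The endpoint itself stands, provided it is described as comfort over the first two weeks on the finalized prescription. The missing minimum interval before Visit 3 is a secondary gap. Its effect depends on how early visits fall and how many powers are changed, and the protocol gives neither. The conclusion on overlap assumes only that visits take place at the stated one and two weeks and that participants answer the CLDEQ-8 as worded.

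**What to change.** 1. In Study Considerations, item 5, delete the long-term clause ("ensuring the data reflects long-term wearability") and stop describing the 14 days as a wash-in for the CLDEQ-8. State instead that the primary endpoint describes the first two weeks on the finalized prescription, about days 8 to 21 of study-lens wear.
2. In the Visit 3 heading and the Study Assessments table, replace the approximate interval with at least 14 full days after the last prescription change, so that the recall holds only the finalized prescription, as the endpoint requires. This has to be set before visits take place, because days on a superseded power cannot be taken out of a recalled score afterwards.
3. State whether the Appendix instruction to rate the most recent pair applies to the CLDEQ-8 as well as to the VAS, and reconcile it with the two-week wording of the items.

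If the sponsor wants to keep a claim about wear after adaptation, Visit 3 has to move later by whatever length of adaptation is to be excluded.

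A descriptive split of the primary proportion by power changed or unchanged at Visit 2 is optional; the point does not depend on it.

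The cost is a few sentences and a one-sided visit window. Some visits will fall a few days later, and the claim becomes narrower.
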